6.2 DURATION OF STUDY PARTICIPATION

6.2.1 Duration of study participation for each patient

The study duration includes a screening period of up to 3 weeks, a 24-week DBTP for efficacy and safety assessment and an 8-week post-treatment follow-up period for all patients after the last visit of the DBTP.

Thus, the study duration per patient is about 35 weeks (up to 3 weeks screening + 24 weeks double-blind treatment + 8 weeks follow-up).

Patients who experience an ongoing SAEs or an adverse event of special interest (AESI), at the pre-specified study end-date, should be followed until resolution, stabilization, or death and related data will be collected.

Patients who have a titer at or above 240 for anti-alirocumab antibody at follow up visit will have additional antibody sample(s), at 6 to 12 months after the last dose and thereafter, about every 3 to 6 months until titer returns below 240.

The end of the study per patient is the last protocol planned visit, or the resolution/stabilization of all SAEs, and AESI, or the resolution of anti-alirocumab (titer below 240), whichever comes last.

6.2.2 Determination of end of clinical trial (all patients)

The end of the study is defined as being the last patient last on site visit as scheduled by protocol.

6.3 STUDY COMMITTEES

Data Monitoring Committee:

An independent DMC, composed of members independent from the Sponsor and the study investigators, is implemented in order to monitor patient safety by conducting formal reviews of accumulated safety data that will be blinded by treatment group; if requested, the DMC may have access to the treatment allocation code or any other requested data for the purposes of a risk-benefit assessment (eg, lipid efficacy data). The DMC will provide the Sponsor with appropriate recommendations on the conduct of the clinical trial to ensure the protection and safety of the patients enrolled in the study. In addition, the DMC will also institute any measures that may be required for ensuring the integrity of the study results during the study execution. All activities and responsibilities of the DMC are described in the DMC charter.

Cardiovascular Events Adjudication Committee:

The CEC is composed of experts in the field of cardiovascular diseases, independent from the Sponsor and the Investigators. This committee will be responsible for defining, validating and classifying, in a blinded fashion, pre-specified cardiovascular events and all deaths. Classification of events will be as follows: CHD death, non-fatal MI, fatal and non-fatal ischemic stroke, unstable angina requiring hospitalization, congestive heart failure requiring hospitalization, and ischemia-driven coronary revascularization procedure (percutaneous coronary intervention [PCI], coronary artery bypass graft surgery [CABG]). In addition, the classification of the cause of all deaths will occur. A charter and an adjudication operational manual will specify the procedures, criteria, and classification used for adjudication of these events.

7 SELECTION OF PATIENTS

7.1 INCLUSION CRITERIA

- I 01. Patients with hypercholesterolemia and established CHD or CHD risk equivalents (see below for definitions) who are not adequately controlled with a maximally tolerated daily dose of statin* at a stable dose for at least 4 weeks prior to the screening visit (Week -3)

*Definition of maximally tolerated dose (any of the following are acceptable):

- Atorvastatin 40 mg to 80 mg daily
- Rosuvastatin 20 mg to 40 mg daily
- Simvastatin 40 mg daily
- Patients not able to be on any of the above statin doses, should be treated with the dose of daily atorvastatin, rosuvastatin or simvastatin which is considered appropriate for the patient as per the investigator's judgment or concerns. Some examples of acceptable reasons for a patient taking a lower statin dose include, but are not limited to: adverse effects on higher doses, advanced age, low body mass index (BMI), local prescribing information, concomitant medications, comorbid conditions such as impaired glucose tolerance/impaired fasting glucose. The reason(s) will need to be documented in the case report form.

A) Documented history of CHD (includes one or more of the following):

- Acute MI
- Silent MI
- Unstable angina
- Coronary revascularization procedure (eg, PCI, CABG)
- Clinically significant CHD diagnosed by invasive or non-invasive testing (such as coronary angiography, stress test using treadmill, stress echocardiography or nuclear imaging)

B) CHD risk equivalents (includes one or more of the following 4 criteria):

- i) Documented peripheral arterial disease (PAD) (one of the following criteria [a, b, or c] must be satisfied):
 - (a) Current intermittent claudication (muscle discomfort in the lower limb produced by exercise that is both reproducible and relieved by rest within 10 minutes) of presumed atherosclerotic origin TOGETHER WITH ankle-brachial index equal to or less than 0.90 in either leg at rest OR
 - (b) History of intermittent claudication (muscle discomfort in the lower limb produced by exercise that is both reproducible and relieved by rest within

- 10 minutes) TOGETHER WITH endovascular procedure or surgical intervention in one or both legs because of atherosclerotic disease OR
- (c) History of critical limb ischemia TOGETHER WITH thrombolysis, endovascular procedure or surgical intervention in one or both legs because of atherosclerotic disease
 - ii) Documented previous ischemic stroke with a focal ischemic neurological deficit that persisted more than 24 hours, considered as being of atherothrombotic origin. CT or MRI must have been performed to rule out primary hemorrhage and non-ischemic neurological disease.
 - iii) Documented chronic kidney disease (CKD) as defined by $30 \leq \text{eGFR} < 60 \text{ mL/min/1.73 m}^2$ for 3 months or more, including the screening visit
 - iv) Known history of diabetes mellitus AND 2 or more additional risk factors (as listed below):
 - (a) History of hypertension (established on antihypertensive medication)
 - (b) Documented history of ankle-brachial index ≤ 0.90
 - (c) Documented history of microalbuminuria or macroalbuminuria ([44](#)) OR dipstick urinalysis at screening visit (Week -3) with $>2 +$ protein
 - (d) Documented history of preproliferative or proliferative retinopathy or laser treatment for retinopathy
 - (e) Known family history of premature CHD (CHD in father or brother before 55 years of age; CHD in mother or sister before 65 years of age)

I 02. Signed written informed consent

7.2 EXCLUSION CRITERIA

Patients who have met all the above inclusion criteria listed in [Section 7.1](#) will be screened for the following exclusion criteria which are sorted and numbered in the following 3 subsections:

7.2.1 Exclusion criteria related to study methodology

- E 01. Patients without established CHD or CHD risk equivalents
- E 02. LDL-C $< 70 \text{ mg/dL} (< 1.81 \text{ mmol/L})$ at the screening visit (Week -3) in patients with an history of documented CV disease
- E 03. LDL-C $< 100 \text{ mg/dL} (< 2.59 \text{ mmol/L})$ at the screening visit (Week -3) in patients without history of documented CV disease

NOTE – CVD is defined as CHD, ischemic stroke or PAD as described in [Section 7.1](#)

- E 04. Change in statin dose or dose regimen from screening to randomization

- E 05. Currently taking a statin that is not atorvastatin, rosuvastatin or simvastatin
- E 06. Atorvastatin, rosuvastatin or simvastatin is not taken daily or not taken at a registered dose
- E 07. Daily dose above atorvastatin 80 mg, rosuvastatin 40 mg or simvastatin 40 mg
- E 08. Use of cholesterol absorption inhibitor (ie, ezetimibe), omega-3 fatty acid (at doses \geq 1000 mg daily), nicotinic acid, fibrates, bile acid-binding sequestrant, or red yeast rice products within the past 4 weeks prior to screening visit (Week -3) or between screening and randomization visits
- E 09. Use of nutraceutical products or over-the-counter therapies that may affect lipids which have not been at a stable dose/amount for at least 4 weeks prior to the screening visit (Week -3) or between screening and randomization visits
- E 10. Patient who has received plasmapheresis treatment within 2 months prior to the screening visit (Week -3), or has plans to receive during the study.
- E 11. History of a MI, unstable angina leading to hospitalization, CABG, PCI, uncontrolled cardiac arrhythmia, carotid surgery or stenting, stroke, transient ischemic attack, carotid revascularization, endovascular procedure or surgical intervention for peripheral vascular disease within 3 months prior to the screening visit (Week -3, V1)
- E 12. Planned to undergo scheduled PCI, CABG, carotid or peripheral revascularization during the study
- E 13. Systolic blood pressure $>$ 160 mmHg or diastolic blood pressure $>$ 100 mmHg at screening visit or randomization visit
- E 14. History of New York Heart Association (NYHA) Class III or IV heart failure within the past 12 months ([Appendix B](#))
- E 15. Known history of hemorrhagic stroke
- E 16. Age $<$ 18 years or legal age of majority at the screening visit (Week -3) whichever is greater
- E 17. Patients not previously instructed on a cholesterol-lowering diet prior to the screening visit (Week-3)
- E 18. Newly diagnosed (within 3 months prior to randomization visit [Week 0]) or poorly controlled ($\text{HbA1c} > 9\%$ at the screening visit [Week -3]) diabetes
- E 19. Presence of any clinically significant uncontrolled endocrine disease known to influence serum lipids or lipoproteins.

NOTE: Patients on thyroid replacement therapy can be included if the dosage has been stable for at least 12 weeks prior to screening and between screening and randomization visits, and thyroid stimulating hormone (TSH) level is within the normal range at the screening visit.

- E 20. History of bariatric surgery within 12 months prior to the screening visit (Week -3)
- E 21. Unstable weight defined by a variation >5 kg within 2 months prior to the screening visit (Week -3)
- E 22. Known history of homozygous or heterozygous FH
- E 23. Known history of loss of function of PCSK9 (ie, genetic mutation or sequence variation)
- E 24. Use of systemic corticosteroids, unless used as replacement therapy for pituitary/adrenal disease with a stable regimen for at least 6 weeks prior to randomization (Week 0)

NOTE: Topical, intra-articular, nasal, inhaled and ophthalmic steroid therapies are not considered as 'systemic' and are allowed

- E 25. Use of continuous estrogen or testosterone hormone replacement therapy unless the regimen has been stable in the past 6 weeks prior to the Screening visit (Week -3) and no plans to change the regimen during the study
- E 26. History of cancer within the past 5 years, except for adequately treated basal cell skin cancer, squamous cell skin cancer or in situ cervical cancer
- E 27. Known history of a positive HIV test
- E 28. Patient who has taken any investigational drugs other than the alirocumab training placebo kits within 1 month or 5 half lives, whichever is longer
- E 29. Patient who has been previously treated with at least one dose of alirocumab or any other anti-PCSK9 monoclonal antibody in other clinical trials
- E 30. Patient who withdraws consent during the screening period (patient who is not willing to continue or fails to return)
- E 31. Conditions/situations such as:
 - Any clinically significant abnormality identified at the time of screening that in the judgment of the Investigator or any Subinvestigator would preclude safe completion of the study or constrain endpoints assessment such as major systemic diseases, patients with short life expectancy.
 - Considered by the Investigator or any Subinvestigator as inappropriate for this study for any reason, eg:
 - Deemed unable to meet specific protocol requirements, such as scheduled visits

- Deemed unable to administer or tolerate long-term injections as per the patient or the investigator
- Investigator or any Subinvestigator, pharmacist, study coordinator, other study staff or relative thereof directly involved in the conduct of the protocol, etc
- Presence of any other conditions (eg, geographic, social) actual or anticipated, that the Investigator feels would restrict or limit the patient's participation for the duration of the study

- E 32. Laboratory findings during the screening period (not including randomization Week 0 labs):
- Positive test for Hepatitis B surface antigen or Hepatitis C antibody (confirmed by reflexive testing)
 - Positive serum beta-hCG or urine pregnancy test (including Week 0) in women of childbearing potential
 - Triglycerides >400 mg/dL (>4.52 mmol/L) (1 repeat lab is allowed)
 - eGFR <30 mL/min/1.73 m²
 - ALT or AST >3 x ULN (1 repeat lab is allowed)
 - CPK >3 x ULN (1 repeat lab is allowed)
 - TSH $<LLN$ or $>ULN$ (1 repeat lab is allowed)

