8.9.1 Management of background lipid modifying therapy / Rescue therapy

Patients must have been on stable maximally tolerated daily registered doses of statins for at least 4 weeks before screening visit.

During the study, the patients should stay on these stable maximally tolerated registered daily doses of statins. Lipid profile values from samples obtained after randomization will be blinded. Nevertheless, sites will be made aware of TG alert, in order to make decisions on the patient's background LMT.

From the screening visit (Week -3) until Week 24 of the DBPT, the background LMT should not be changed. No dose adjustment, discontinuation or initiation of other statins should take place during this time, barring exceptional circumstances whereby overriding concerns (including but not limited to TG alert posted by the central lab) warrant such changes, as per the investigator's judgment.

For a TG alert (see [Section 10.6.4](#)) that has been confirmed by repeat testing, the investigator should perform investigations, manage the patient, and modify the background LMT as per his/her medical judgment.

In summary, background statin therapy should not be modified from screening to the follow up visit. However, up to Week 24, if a confirmed TG alert is reached or if there is an overwhelming clinical concern (at the discretion of the investigator) then modification of the background LMT is allowed.

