8.9.3 Prohibited concomitant medications

Forbidden concomitant medications from the initial screening visit until the randomization visit include the following:

- Statins other than atorvastatin, rosuvastatin and simvastatin
- Fibrates
- Cholesterol absorption inhibitor (ie, ezetimibe)
- Omega-3 fatty acid (at doses ≥ 1000 mg daily)
- Nicotinic acid
- Bile acid-binding sequestrant (such as cholestyramine, colestipol, colesevelam)
- Red yeast rice products

Forbidden concomitant medications after the randomization visit until the follow up period include the following:

- Statins other than atorvastatin, rosuvastatin and simvastatin
- Fibrates (except fenofibrate if patient meets the prespecified TG alert [TG ≥ 500 mg/dL (5.65 mmol/L)])
- Cholesterol absorption inhibitor (ie, ezetimibe)
- Omega-3 fatty acid (at doses ≥ 1000 mg daily)
- Bile acid-binding sequestrant (such as cholestyramine, colestipol, colesevelam)
- Red yeast rice products

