## Appendix B Detailed statistical methodology for pattern mixture model

As a sensitivity analysis of the primary efficacy endpoint (i.e. percent change from baseline to Week 24 in calculated LDL-C), a pattern-mixture model approach will be used, with a different imputation strategy applied for missing calculated LDL-C values during the on-treatment period (ie, within the time period from the first double-blind IMP injection up to the day of the last injection +21 days) and missing calculated LDL-C values after treatment discontinuation (ie, after the day of last injection +21 days) based on the following assumptions:

- Patients within 21 days of their last IMP injection would continue to show benefit from treatment similar to that observed at the scheduled time point. Therefore, calculated LDL-C values missing during the on-treatment period will be considered “Missing At Random” and imputed using a model estimated using all samples collected on treatment.
- Patients who stopped taking their study treatment no longer benefited from it in the future, and thus tended to have calculated LDL-C values returning to baseline. Thus calculated LDL-C values missing after treatment discontinuation will be imputed based on patient’s own baseline value.

The assumptions for this approach are based on the following considerations:

- Missing values during the on-treatment period are mostly consecutive to:
  - Visits performed outside of the pre-specified time-window
  - No blood sample available although visit was done
  - Calculated LDL-C not measurable due to technical reasons

In addition, these missing data are often intermittent, i.e. followed by calculated LDL-C values collected at subsequent visits. It is therefore considered reasonable to assume that these missing data were “At Random”.

- Phase 2 studies DFI11565 and R727-CL-1003 included a prospective assessment of calculated LDL-C during the follow-up period after a 12-week treatment period. These studies showed that after treatment discontinuation, the average calculated LDL-C returned to baseline level within 4 weeks after ceasing alirocumab treatment.

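### Exclusion E29 reaches prior anti-PCSK9 antibody use only if it came from another trial, so recent prescribed use can depress the LDL-C baseline (minor)

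*Protocol*

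**What the plan says.** E29 in Protocol Section 7.2.1 excludes a "Patient who has been previously treated with at least one dose of alirocumab or any other anti-PCSK9 monoclonal antibody in other clinical trials". The neighbouring text does not extend this to prescribed use:

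- E28 excludes a "Patient who has taken any investigational drugs other than the alirocumab training placebo kits within 1 month or 5 half lives, whichever is longer", so its washout concerns investigational drugs.
- E08 opens with "Use of cholesterol absorption inhibitor (ie, ezetimibe), omega-3 fatty acid" and goes on to nicotinic acid, fibrates, bile acid sequestrants and red yeast rice, with a 4-week look-back before screening. Anti-PCSK9 antibodies are not listed.
- Section 8.9.3 has two lists. One is introduced by "Forbidden concomitant medications from the initial screening visit until the randomization visit include the following", the other by "Forbidden concomitant medications after the randomization visit until the follow up period include the following". Neither names the class.
- Section 8.9 permits concomitant drugs that the patient needs and that are unlikely to interfere with the IMP. It then says that any other concomitant medication is allowed and must be recorded.
- Section 8.9.1 adds: "From the screening visit (Week -3) until Week 24 of the DBPT, the background LMT should not be changed".

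On timing, screening falls 8 to 21 days before randomization (Section 10.1.1), and baseline is the last LDL-C before the first double-blind dose (Section 9.1.1). On offset of effect, SAP Appendix B reports from phase 2 follow-up that "the average calculated LDL-C returned to baseline level within 4 weeks after ceasing alirocumab treatment". Protocol Section 9.2 expects residual effect until 10 weeks after stopping.

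**The concern.** Read literally, one trial dose at any time in the past excludes a patient, while a prescribed dose the week before screening does not. Where the drug came from has no bearing on LDL-C, so the criterion misses part of its evident purpose. The drug class under test is left without the washout that E08 gives to the other non-statin lipid therapies.

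Two things could follow. A recently treated patient could be randomized with a baseline already lowered by the study drug's own mechanism, and that baseline is the denominator of the primary endpoint. A patient who stays on the prescribed antibody could receive two agents of the same class. Neither case would breach a named criterion, so neither need appear as a protocol deviation. The sensitivity and subgroup analyses in SAP Sections 2.4.4.1.3 to 2.4.4.1.6 do not look for such patients, and the list of prior lipid therapies in SAP Section 2.1.1 could hold the class only under its residual category.

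**Working it through.** **1. The plan's own figure.** Protocol Section 11.1 gives 64 versus 32 patients, difference 20 points, SD 25, two-sided 0.05. A noncentral-t calculation gives 95.5% power; 62 versus 31 gives 94.9%. So 96 is the smallest 2:1 total reaching 95%, and the figure reproduces. At the actual 400:200, SE = 25 × √(1/400 + 1/200) = 2.17 points.

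**2. How far carry-over reaches.** A stopped antibody was last given before Week 0, so at least 24 weeks separate it from the Week 24 sample. That exceeds both the 4-week average return to baseline and the 10-week outer limit. The Week 24 value is clean. The Week 0 value is not, if the last dose fell within about 4 weeks before it (10 at most).

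**3. Entry floors.** With LDL-C halved, a patient must have an unsuppressed level of at least 70/0.5 = 140 mg/dL (with CVD, E02) or 100/0.5 = 200 mg/dL (without, E03).

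**4. Distortion per affected patient.** The effects come from the design rationale in Protocol Section 4: alirocumab about 50%, ezetimibe 25% to 30%. Using 30% gives the planned 20-point difference. Let L be LDL-C on statin alone, and assume the other antibody also lowers it by 50%.

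- *Stopped, fully suppressed baseline of 0.5L.* Alirocumab: 0.5L/0.5L − 1 = 0%. Ezetimibe: 0.7L/0.5L − 1 = +40%. The advantage is 40 points instead of 20, an excess of 20. With ezetimibe at 25%, the figures are +50%, 50 instead of 25, an excess of 25.
- *Stopped, baseline suppressed by 25%.* Alirocumab: 0.5/0.75 − 1 = −33.3%. Ezetimibe: 0.7/0.75 − 1 = −6.7%. The advantage is 26.7 points.
- *Continued, alirocumab adding nothing (worst case).* Alirocumab 0%, ezetimibe −30%. The advantage is −30 instead of +20, a shift of 50. With ezetimibe at 25% it is −25 instead of +25, again 50.

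**5. Effect on the trial.** The share affected, f, is an assumption, taken as equal in both arms. Trial advantage = (1 − f) × 20 + f × D, with D = 40 (stopped, fully suppressed) or −30 (continued).

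| f | Stopped: advantage (SE) | Continued: advantage (SE) |
|---|---|---|
| 0 | 20.0 (2.17) | 20.0 (2.17) |
| 1% | 20.2 (2.27) | 19.5 (2.18) |
| 5% | 21.0 (2.62) | 17.5 (2.23) |
| 10% | 22.0 (2.98) | 15.0 (2.29) |
| 20% | 24.0 (3.52) | 10.0 (2.39) |

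With only 25% suppression, the stopped case at 5% gives 0.95 × 20 + 0.05 × 26.7 = 20.3. Power at 600 patients is 98.7% in the worst cell (continued, 20%) and above 99.9% in the others. These are unadjusted means; the effect of the baseline covariate in the MMRM was not modelled.

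**The case against.** The strongest reply is that no exposed population is shown. The introduction's list of current LDL-C-lowering drugs contains no anti-PCSK9 antibody, and Section 11.1 sets the 600 partly to meet registration requirements in the participating countries. Use may have been close to nil. That stands, and it limits the importance of the point.

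There are also real barriers. Section 8.9 has its non-interference condition, E31 lets the investigator exclude a patient as unsuitable for any reason, and 12 weeks of prior lipid therapy are documented at screening. The synopsis restricts adding lipid therapy during double-blind treatment. The entry floors remove many fully suppressed patients, and known familial hypercholesterolemia is excluded by E22. All of this narrows the gap without closing it. E31 is discretion, the synopsis speaks of adding rather than continuing, and the non-interference condition in 8.9 sits beside a general permission.

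Section 8.9.1 might be read as requiring a prescribed antibody to be continued. The documents do not support that. Section 8.2 names only statins and fenofibrate as background or potential rescue products, and the trial is described throughout as add-on to statin.

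A reader might also infer that the antibody analysis is badly compromised. SAP Section 2.1.6 measures ADA at baseline and separates pre-existing from treatment-emergent responses by a 4-fold titer rule, so most of that concern is already met.

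**Conclusion.** The wording gap is real and of minor importance. Under the criteria as written, a patient recently or currently on a prescribed anti-PCSK9 antibody can be enrolled. If the drug was stopped shortly before Week 0, baseline is suppressed and percent change is distorted at every visit. If it is continued, the Week 24 value itself is affected, but through concomitant exposure rather than carry-over.

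Two stronger conclusions are tempting and should not be drawn. One is that carry-over from earlier use contaminates the Week 24 LDL-C value; the documents' own 4-week and 10-week figures rule that out. The other is that the primary conclusion is in doubt. At an assumed 1% to 5% affected, the planned 20-point difference moves by +0.2 to +1.0 points (stopped, ezetimibe effect 30%) or −0.5 to −2.5 points (continued, alirocumab adding nothing), and power stays at about 99% or more even at 20%. The two cases push in opposite directions, so the net sign cannot be stated.

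These sizes rest on the protocol's expected effects, an equal 50% effect of the other antibody, equal shares in both arms, and an exposure rate that the documents do not give.

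**What to change.** Delete the closing four-word phrase of E29 that confines it to other trials, so that prior exposure from any source is covered. Reconcile both lists in Section 8.9.3 with the revised criterion; amending only the list that runs up to randomization would leave the double-blind period unaddressed.

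The SAP already describes randomization in the past tense, with the first patient randomized on 11 August 2016. If enrolment is complete, the eligibility edit no longer helps. In that case, list any exposed patients from the 12-week prior-medication record and add one sensitivity analysis that reruns the primary MMRM without them. If there are none, a sentence in the study report settles the matter.

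The cost is a few words in one criterion and two lists, with at most a handful of screen failures, or one listing and one rerun of an existing model. The sample size is unaffected.
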